#### **Definition of line of therapy:**

1st line: no prior use of any DMARD at time of initiation

2nd line: prior use of at least one csDMARD and no prior use of any biologic

3rd line: prior use of at least one csDMARD and prior use of 1 biologic

4th line+: prior use of at last one csDMARD and prior use of 2+ biologics

#### **2.4.5. Time Periods**

##### Study visits

The Corrona RA registry is an observational registry collecting patient and physician data at regular patient clinical visits with the rheumatologist. Unlike in clinical trials, visits are not timed at exact uniform time periods. We will define the 6-month visit as a Corrona visit that occurs between 3-9 months post- index visit. We will define the 12 month visit as a Corrona visit that occurs between 10-15 months post index visit. If the patient had more than one visit in the

window between 3 and 9 months (or 10-15 months), the visit closest to 6 (or 12) months will be selected.

## **2.4.6. Variables**

### **For Objective 1 (Demographics, clinical characteristics, treatment patterns):**

#### *Demographic/socioeconomic characteristics*

- Age, sex, race, education, work status, insurance

#### *Lifestyle*

- Weight, body mass index(BMI), smoking status

#### *History of comorbidities*

- History of CV disease (include the following: MI, stroke, acute coronary syndrome, coronary artery disease, CHF, revascularization procedure including percutaneous coronary intervention [PCI], coronary artery bypass grafting [CABG] or coronary artery stents, ventricular arrhythmia, cardiac arrest, unstable angina, peripheral ischemia, peripheral arterial disease, hypertension, other CV, DVT, and TIA.)
- History of malignancy (breast cancer, lung cancer, lymphoma, skin cancer, other cancer)
- History of hypertension, diabetes, osteoporosis, fibromyalgia, and depression

#### *Clinical Characteristics and Assessments*

- Duration of disease
- Age of onset
- CDAL (continuous, categorical)
- Tender joint count (28)
- Swollen Joint count (28)
- Physician global assessment (0-100)
- DAS28(ESR)
- Patient global assessment (0-100)
- Patient reported pain (0-100)
- Patient reported fatigue (0-100)
- HAQ (0-3)
- mHAQ
- Morning stiffness (yes/no)
- Morning stiffness duration (hours)

#### *Treatment Characteristics and Medication history*

- Concomitant therapies (Monotherapy, Combo with: MTX alone, other CDMARD, MTX + other CDMARD)

- Number of prior biologics/JAKis (TNFi: Enbrel, Humira, Remicade, Cimzia, Simponi; non-TNFi: Orencia, Actemra, Rituxan, Kineret, Kevzara; JAKis: Olumiant, Rinvoq)
- Number of prior csDMARDs (MTX, Arava, Azulfidine, Plaquenil, Cyclosporine, Imuran, Minocin, Cuprimine, Ridaura)
- Steroid use
  - History of prednisone use (yes/no)
  - Current prednisone use (yes/no)
  - Prednisone dose (in users)
- Mode of Action (MOA) History
  - TNF inhibitor
  - Non-TNF inhibitor
  - csDMARDs
  - tsDMARDs
- History of treatment of MOA (Ever)
  - TNF inhibitor
  - Non-TNF inhibitor
  - csDMARDs
  - tsDMARDs

*Reason for initiation of Tofa:*

- Number of patients with at least 1 initiation reason reported
- Total number of reasons
- % Safety, % Efficacy, % Cost/Insurance, %Other reasons

*Reason for Discontinuation of tofa (Among those who discontinue at or before 6-months):*

- Total number (%) of discontinuations
- Number of patients with at least 1 reason reported
- Total number of reasons
- % Safety, % Efficacy, % Cost/Insurance, %Other reasons

**For objective 2 (6-months effectiveness) and objective 3 (12-months effectiveness)**

*Primary outcomes:*

- Achievement of LDA (CDAI  $\leq$  10)

*Secondary outcomes:*

- Achievement of remission (CDAI  $\leq$  2.8)
- $\Delta$  CDAI
- $\Delta$  HAQ

- $\Delta$  patient pain
- $\Delta$  patient fatigue
- Achievement of mACR20/50/70
- Achievement of LDA or remission defined by DAS28(ESR) ( $\leq 3.2$ )
- Achievement of “mild pain”, defined as  $\leq 20$ mm on 100 VAS scale

## 2.5. Plan of Analysis

### Definitions:

Index visit (Baseline): The Corrona visit with the first reported use of tofa.

Disease activity measures and patient-reported outcomes (PROs) from the index (baseline) visit will be used if the initiation date is the same as the visit date. If tofa is initiated between visits, and the prior visit is within 4 months of the initiation date, disease activity measures and PROs from the prior visit will be used as the baseline value.

### Line of therapy:

1st line: no prior use of any DMARD at time of initiation

2nd line: prior use of at least one csDMARD and no prior use of any biologic

3rd line: prior use of at least one csDMARD and prior use of 1 biologic

4th line+: prior use of at least one csDMARD and prior use of 2+ biologics

### Study Cohorts:

- Overall tofa initiators who meet inclusion criteria
- Tofa monotherapy at initiation visit (tofa only)
- Tofa combo therapy at initiation visit (tofa+MTX, Arava, Azulfidine, Plaquenil, or cyclosporine)
- Tofa initiators by line of therapy in 2nd line, 3rd line and 4th line
- Tofa dose of 5mg, twice a day at initiation visit
- Tofa dose of 11mg, once a day at initiation visit
- Tofa initiators by year of initiation (2012-2014, 2015-2017, 2018-2020)

This project will be separated into 4 milestones:

1. Analysis in overall tofa initiators, and monotherapy v. combination therapy
2. Analysis by line of therapy in 2nd line, 3rd line and 4th line
3. Analysis by tofa dose (5mg v. 11mg)
4. Analysis by three time periods of initiation (2012-2014, 2015-2017, 2018-2020)

### **2.5.1. Descriptive analysis**

Baseline patient demographics and clinical characteristics of (listed in [section 2.4.4](#)) will be presented. For categorical variables, n(%) will be presented, and for continuous variables, means, standard deviation (SD), median, 25th and 75ths quartile values will be presented in overall tofa initiators, and by group (for each milestone). P-values will be estimated using student-t test for continuous variables between two comparison groups, one-way Anova for continuous variables among three comparison groups and chi-square test for categorical variables. Two sets of baseline tables will be reported – one for patients with 6 months follow-up and one for patients with 12 months follow-up.

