8. RESEARCH QUESTION AND OBJECTIVES

The objective of this study is to describe treatment patterns and effectiveness of tofacitinib initiators in the Corrona RA Registry. Accordingly, we will:

• Describe the demographics clinical characteristics, and treatment patterns of tofacitinib initiators at the time of initiation including stratification by index year to identify changes across time.

• Estimate 6-month and 12-month effectiveness in tofacitinib initiators.

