9. RESEARCH METHODS

9.1. Study Design

To meet the study objectives, an observational retrospective cohort study will be conducted using patients enrolled in the Corrona RA Registry initiating to facitinib on or after November 2012. NOTE: Initiation is defined as first ever use of to facitinib. Initiators will also be required to have initiated to facitinib at a Corrona visit (enrollment or follow-up), have Clinical Disease Activity Index (CDAI) measured at baseline and have a 6-month follow-up visit and CDAI measured at the 6-month follow-up visit.

For further details, please refer to the detailed Statistical Analysis Plan (SAP) included as a stand-alone document.

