9.2.1. Inclusion Criteria

Patients must meet all of the following inclusion criteria to be eligible for inclusion in the study:

- 1. Enrolled in the Corrona RA Registry and initiated to facitinib on or after November 2012.
- 2. Initiate tofacitinib (defined as first ever use of tofacitinib) at the Corrona enrollment visit or at a Corrona follow-up visit from November 2012 onward.
- 3. Have CDAI measured at baseline.
- 4. Have at least a 6-month follow-up visit and CDAI measured at the 6-month follow-up visit.

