#### 2.2.1. *Objective 1*

To describe the demographics, clinical characteristics, and treatment patterns of tofa initiators at time of initiation.

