### **2.4.3. Study Populations**

#### *Inclusion Criteria*

For this analysis patients must:

1. Initiate tofa (defined as first ever use of tofa) at the Corrona enrollment visit or at a Corrona follow up visit from November 2012 onward.
2. Have CDAI measured at baseline.
3. Have a 6-month or 12-month follow-up visit and CDAI measured at 6-month or 12-month follow-up visit

Note: Additionally, the specified populations will be used to calculate each of the following variables.

- Achievement of LDA (CDAI≤10).
  - Among patients with moderate or high disease activity (CDAI>10) at baseline.
- Rate of response at follow up visit-achievement of remission (CDAI≤2.8).
  - Among patients with LDA, moderate, or high disease activity (CDAI>2.8) at baseline.
- Achievement of LDA or remission defined by DAS28(ESR) (<= 3.2)
  - Among patients who have DAS28>3.2 at the initiation visit.
- Achievement of “mild pain”, defined as ≤ 20mm on 100 VAS scale
  - Among patients who have pain >20 mm on 100 VAS at the initiation visit

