### 3. Shell Tables

Milestone 1: Results for tofa monotherapy and combination therapy

Milestone 2: Results for line of therapy (2nd, 3rd, 4th line)

Milestone 3: Results for tofa dose (5mg and 11mg)

Milestone 4: Results for tofa initiation time periods (2012-2014, 2015-2017, and 2018-2020)

Table 1. Demographic and clinical characteristics at tofa initiation visit, overall and for monotherapy and combination therapy in patients with 6 months follow up.

	All Patients	Tofa monotherapy	Tofa combination therapy ‡	P-value*
	N=	N=	N=	
Demographic/socioeconomic characteristics				
Age: Mean±SD				
Median (IQR)				
Female: n(%)				
Race/Ethnicity: n(%)				
White				
Hispanic				
Black				
Asian				
Other				
Type of Insurance:				
None: n (%)				
Private: n (%)				
Medicare: n (%)				
Medicaid: n (%)				
Final education: n(%)				
Primary				
High school				
College/Univ.				
Unknown				
Work Status: n(%)				
Full Time				
Part Time				
Disabled				

Retired				
Other				
Lifestyle				
Smoking status: n(%)				
Never				
Previous				
Current				
Weight (lb): Mean±SD				
Median (IQR)				
BMI: Mean±SD				
Median (IQR)				
History of comorbidities: n(%)				
Cardiovascular disease**				
Malignancy***				
Hypertension				
Diabetes				
Osteoporosis				
Fibromyalgia				
Depression				

\* T-tests will be used to evaluate mean differences between groups for continuous variables, and Chi-square tests will be used to evaluate differences between treatment groups for categorical variables

\*\* included: MI, stroke, TIA acute coronary syndrome, coronary artery disease, CHF, revascularization procedure including percutaneous coronary intervention [PCI], coronary artery bypass grafting [CABG] or coronary artery stents, ventricular arrhythmia, cardiac arrest, unstable angina, other CVs, carotid artery disease.

\*\*\* History of lung cancer, breast cancer, lymphoma, skin cancer (melanoma and squamous), and other cancer

‡ Combination therapy refers to tofa+MTX, arava, azulfidine, plaquenil, or cyclosporine

Table 2. RA disease characteristics, disease activity measures and PROs at tofa initiation visit, overall and for monotherapy and combination therapy in patients with 6 months follow up.

	All Patients	Tofa Monotherapy	Tofa Combination Therapy ‡	P value*
	N=	N=	N=	
RA disease characteristics				
Duration of RA: Mean±SD				
Median (IQR)				
Age onset RA: Mean±SD				
Median (IQR)				

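### Objective 1 is to describe initiators at initiation and across index years, but every planned baseline and reason-for-initiation table is limited to patients who returned with a CDAI

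*SAP*

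**What the plan says.** **Objective.** Protocol section 8 sets out to cover patient features at the start of treatment and, in its own words, "treatment patterns of tofacitinib initiators at the time of initiation including stratification by index year to identify changes across time". SAP 2.2.1 has the same aim without the index-year clause: "To describe the demographics, clinical characteristics, and treatment patterns of tofa initiators at time of initiation". Neither sentence attaches a follow-up condition.

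**Population.** Protocol 9.1 says initiators must also "have a 6-month follow-up visit and CDAI measured at the 6-month follow-up visit", and criterion 4 in Protocol 9.2.1 repeats this: "Have at least a 6-month follow-up visit and CDAI measured at the 6-month follow-up visit". Criterion 3 in SAP 2.4.3 is wider: "Have a 6-month or 12-month follow-up visit and CDAI measured at 6-month or 12-month follow-up visit". In SAP 2.5 the overall cohort is defined as "Overall tofa initiators who meet inclusion criteria".

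**Tables.** SAP 2.5.1 plans two baseline sets, "one for patients with 6 months follow-up and one for patients with 12 months follow-up". The title of Table 1 is "Demographic and clinical characteristics at tofa initiation visit, overall and for monotherapy and combination therapy in patients with 6 months follow up", and Tables 2 and 3 are limited in the same way. Tables 6-20 repeat Tables 1-5 by line of therapy, dose and initiation period. Tables 21-40 repeat everything for the 12-month set.

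**Limitations.** Protocol 9.9 covers how far the registry represents US patients, visit windows, adherence, and missing demographic data. It does not say that initiators without a follow-up CDAI are left out.

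**The concern.** The rationale in Protocol section 7 and SAP 2.1 is that tofacitinib may have moved to an earlier line of therapy. Line of therapy, prior drugs, concomitant therapy and reason for starting are all known at the index visit and need no follow-up. If the plan is followed exactly, the question about changing use is answered only in patients who came back and had a CDAI recorded.

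If initiators who did not return differ from those who did, and if that difference varies by calendar period, the description across index years could be distorted. As planned, the report would give no means of judging this. Reasons for discontinuation (Table 4) do need later information and are not part of this point.

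**Working it through.** **Inputs.** All counts are from SAP 2.4.4, as of 31 August 2020: 2744 initiators, 1650 in the 6-month set and 1223 in the 12-month set, both with baseline and follow-up CDAI. The visit windows, 3-9 and 10-15 months, are from SAP 2.4.5.

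**1. The plan's totals reproduce.** By therapy: 730 + 920 = 1650 and 536 + 687 = 1223. By period: 451 + 725 + 474 = 1650 and 349 + 597 + 277 = 1223. The step from 2744 to these totals is a registry count and cannot be re-derived from the documents.

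**2. Share in each set.**
- 6-month set: 1650/2744 = 60.1%, leaving 1094 (39.9%) outside.
- 12-month set: 1223/2744 = 44.6%, leaving 1521 (55.4%) outside.

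**3. Initiators described in no table.** This depends on which criterion applies.
- Protocol (6-month visit required): 2744 - 1650 = 1094.
- SAP (6- or 12-month visit): 2744 - (1650 + 1223) + overlap. The overlap is not given. It can run from 1650 + 1223 - 2744 = 129 up to 1223, so the number is 0 to 1094. Zero would need only 129 of the 1223 (10.5%) to have a 6-month visit as well.
- If having one visit is independent of having the other (an assumption): 1094 × 1521/2744 = 606 (22.1%). Positive association gives more, up to 1094.

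**4. How much of the 1094 could be lack of time.** Assume that all 2744 are eligible, that starts are uniform over the 32 months from January 2018 to August 2020, and that patients with enough time enter the 6-month set with the same probability c in every period. The two earlier periods contribute 451 + 725 = 1176.
- Time needed until the window opens (3 months): 474 × 32/29 = 523.0; c = (1176 + 523.0)/2744 = 0.619; recent starts = 523.0/0.619 = 845; without time = 845 × 3/32 = 79.
- Time needed until the window closes (9 months): 474 × 32/23 = 659.5; c = (1176 + 659.5)/2744 = 0.669; recent starts = 659.5/0.669 = 986; without time = 986 × 9/32 = 277.

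On these assumptions 79 to 277 of the 1094 simply lacked time, and 33% to 38% of those with time are still outside the 6-month set.

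**5. Do the period counts show uneven selection?**

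| Initiation period | 6-month set | 12-month set | Ratio |
|---|---|---|---|
| 2012-2014 | 451 | 349 | 77.4% |
| 2015-2017 | 725 | 597 | 82.3% |
| 2018-2020 | 474 | 277 | 58.4% |

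The earlier periods pooled give 946/1176 = 80.4%. With uniform recent starts, the snapshot date alone scales this by 17/23 (windows closed) to 22/29 (windows open), giving 59.5% to 61.0% against 58.4% observed. The low recent ratio is therefore largely explained by the date of the count. The two sets need not be nested under the SAP criterion, so these ratios are not retention rates either.

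**6. Possible effect on the key descriptor.** The second-line share is 236/1596 = 14.8% in the 6-month set and 168/1183 = 14.2% in the 12-month set. If a fraction f of initiators is in neither set and their share differs by d points, the all-initiator share moves by f × d. With d = 10 (an assumption):
- f = 0.399 gives 4.0 points.
- f = 0.221 gives 2.2 points.
- f = 0 gives no change.

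This is an overall shift. The shift within each period cannot be computed, because the documents do not give initiators per period.

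**The case against.** The strongest reply is that the restriction is a disclosed and consistent design choice. Protocol 9.1 introduces the follow-up requirement as the way to meet the study objectives, in the plural, and SAP 2.5 defines the overall cohort by the criteria. On that reading, initiators in Objective 1 means this cohort. Both documents also say that the work will inform later comparative effectiveness analyses, for which patients with an evaluable CDAI are a sensible group. The second-line shares in the two sets are close.

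Much of this stands. The restriction is not hidden, and labelling is part of the problem. But disclosure does not make a description of returners answer a question about use at initiation when the data for all initiators are already in the registry. The close second-line shares are weak evidence, because the two sets can overlap and both consist of returners.

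Three stronger readings are tempting, and the documents do not support them:
- *There is no all-initiator count anywhere.* SAP 2.4.4 gives one. It is a feasibility figure, not a planned output, and it lacks reasons for exclusion and a split of the 2744 by period.
- *1094 eligible patients are lost.* SAP 2.4.4 does not say that all 2744 were first-ever users who started at a registry visit from November 2012. It does not separate missing baseline CDAI, no visit in the window, missing follow-up CDAI and too little elapsed time. Data collection ends on 30 November 2021 (Protocol section 6), 15 months after the count. If the final extract runs to that date, the elapsed-time part disappears for these 2744.
- *The period counts show differential selection.* Step 5 shows that the snapshot date accounts for most of the pattern.

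**Conclusion.** The point holds as a mismatch between Objective 1 and the tables that serve it. Every baseline and reason-for-initiation table, including those by initiation period, is conditional on a later CDAI visit; no planned table covers all initiators; and Protocol 9.9 does not name the selection. These facts can be read directly from the documents.

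The consequence is less certain. At the August 2020 count, 39.9% of initiators are outside the 6-month set. Those in neither set number 1094 under the Protocol criterion and anywhere from 0 to 1094 under the SAP criterion. An assumed 10-point difference would move the second-line share by at most 4.0 points overall. This is a selection risk of unknown size and direction, not a demonstrated bias. A low-cost improvement is warranted.

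**What to change.** 1. Apply the follow-up CDAI criterion only to the effectiveness objectives and the existing 6- and 12-month baseline sets (Protocol 9.1 and 9.2.1; SAP 2.4.3 and 2.5.1). Do not add a follow-up CDAI requirement to Table 4, since discontinuation needs a later report but not a CDAI.
2. Add Tables 1-3 and 16-18 for all first-ever initiators who meet SAP criterion 1, with n per item. Report disease activity and patient-reported outcomes among those with data. State whether starts between visits, for which SAP 2.5 has a baseline rule, count under criterion 1.
3. Add a flow count from the final data extract, not from the 2744, overall and by initiation period: initiators, baseline CDAI available, 6- and 12-month windows closed by the data cut, in the 6-month set, in the 12-month set, in neither.
4. Add one table comparing initiators in either set with those in neither.
5. Name the selection as a limitation in Protocol 9.9.

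**Cost.** About six extra tables, one comparison table, one flow count and wording changes in both documents, with no new data collection. The downside is more missing values for disease activity items among initiators without a baseline CDAI.

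**Minimum.** If the tables are not added, reword Objective 1 in Protocol section 8 and SAP 2.2.1 so that it refers to initiators with a follow-up CDAI visit, and keep items 3 and 5.

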### **2.5.2. Effectiveness Analysis**

#### **Primary outcome analyses**

We will estimate the rate of response at 6 and 12 months. Response is defined as the achievement of LDA (CDAI≤10) in patients with moderate or high disease activity (CDAI>10) at baseline. Patients who discontinue tofa within 6 (or 12) months and switch to another biologic or JAK will be considered “non-responders”. Effectiveness outcomes at the 6- and 12- month visits will be estimated in overall tofa initiators and by groups for each milestone. We will report the rate of response and 95% CI for the proportion of response, for patients overall and for each group in [table 5](#).

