#### **Secondary outcomes analysis**

The following secondary outcomes will be considered:

- Rate of response at follow up visit-achievement of remission (CDAI≤2.8) in patients with LDA, moderate, or high disease activity (CDAI>2.8) at baseline. Patients who discontinue tofa within 6 months and switch to another biologic or JAK will be considered “non-responders”.
- Mean of change in CDAI from baseline to follow up visit (6/12). Change in CDAI will be calculated by subtracting baseline CDAI from CDAI measured at 6 months. If a patient discontinues tofa but does not switch to another biologic, the CDAI value at follow up visit (6/12) will be used. If a patient discontinues tofa and switches to another biologic or JAK, the CDAI value at the switch visit will be used for change in CDAI calculation.
- HAQ (HAQ):  
Mean change of HAQ from index date to follow-up visit

- Patient pain (0-100 VAS scale):  
Mean change in pain from index date to follow-up visit
- Patient fatigue (0-100 VAS scale):  
Mean change in fatigue from index date to follow-up visit
- Achievement of modified ACR (mACR)20, mACR50, mACR70
- Achievement of LDA or remission defined by DAS28(ESR) ( $\leq 3.2$ ) in those patients who have DAS28 $>3.2$  at the initiation visit
- Achievement of “mild pain”, defined as  $\leq 20$ mm on 100 VAS scale in those patients who have pain  $>20$  mm on 100 VAS at the initiation visit

Mean changes, rates of response, and corresponding 95% confidence intervals will be reported in total and in each group [Table 5].

Two sets of analyses will be report based on patient with 6 month follow up and patients with 12 months follow up.

All statistical analyses will be performed using STATA Version 15.1 (StataCorp, LLC, College Station, TX).

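### The switcher rule for LDA stops at nominal month 6 or 12 while the visit window runs to month 9 or 15, and the remission rule names only month 6, so some responses on the next drug can count for tofacitinib

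*SAP*

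**What the plan says.** **Primary response (SAP 2.5.2, Primary outcome analyses).** "Response is defined as the achievement of LDA (CDAI≤10) in patients with moderate or high disease activity (CDAI>10) at baseline". The switcher rule follows: "Patients who discontinue tofa within 6 (or 12) months and switch to another biologic or JAK will be considered “non-responders". Its only time limit is the nominal month.

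**Visit windows (SAP 2.4.5, Study visits).** "We will define the 6-month visit as a Corrona visit that occurs between 3-9 months post- index visit", and "We will define the 12 month visit as a Corrona visit that occurs between 10-15 months post index visit". With several visits in the "window between 3 and 9 months (or 10-15 months), the visit closest to 6 (or 12) months will be selected".

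**Remission (SAP 2.5.2, Secondary outcomes analysis).** The same kind of switcher rule is given, but with a limit of 6 months only. The section then plans two sets of analyses, at 6 and 12 months, and the shell tables repeat Table 5 for the 12-month patients.

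**Change in CDAI (same section).** For patients who switch, "the CDAI value at the switch visit will be used for change in CDAI calculation". The bullet concerns change to the 6- or 12-month follow-up visit; the switch sentence gives no limit of its own.

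**Registry visits (Protocol 9.4).** A new biologic, biosimilar or JAK inhibitor prescribed or first given at a routine office visit triggers an early registry visit with questionnaires.

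**The concern.** The switcher rule exists so that disease activity measured on the next drug is not credited to tofacitinib. It does that only if its time limit reaches the day the CDAI is taken. Here the limit is the nominal month, while the CDAI can be up to three months later. Nothing in the LDA definition bars a CDAI recorded after a switch, so a patient can be counted as a tofacitinib responder while on another agent.

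The remission rule raises a second problem of the same kind. With month 6 as its only limit, it leaves patients who stop and switch between months 6 and 12 uncovered at the 12-month analysis, although the LDA rule covers them. CDAI ≤2.8 implies CDAI ≤10, so such a patient could be in remission in Table 5 without being in LDA.

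At stake is who counts as a responder for the primary outcome and the main secondary binary outcome, in work that SAP 2.1 says will inform later comparative effectiveness analyses.

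**Working it through.** **1. The plan's own counts.** SAP 2.4.4 gives 1650 patients with a 6-month visit and 1223 with a 12-month visit. The therapy subgroups reproduce them: 730 + 920 = 1650 and 536 + 687 = 1223. There is no power calculation to reproduce.

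**2. How much of each window lies after the cut-off.** 6-month: (9 − 6)/(9 − 3) = 50%. 12-month: (15 − 12)/(15 − 10) = 60%.

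**3. Timelines under the SAP rules as written.**

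| Stop and switch | Visits in window | Visit selected | Switcher rule applies? | CDAI taken on new drug? |
|---|---|---|---|---|
| 6.5, between visits | 8.5 | 8.5 | No | Yes |
| 6.5, between visits | 3.2 and 8.5 | 8.5 | No | Yes |
| 12.5, between visits | 14.5 | 14.5 | No | Yes |
| 7, at a registry visit | 7 and 8.5 | 7 | No | No |
| 13, at a registry visit | 13 and 14.8 | 13 | No | No |
| Stop 5, switch 7 between visits | 8.5 | 8.5 | Unclear | Yes |

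The first three rows show the gap. Rows four and five show the protection: a switch visit after the nominal month is always closer to it than any later visit, so if CDAI was recorded there it is preferred to any post-switch visit. The last row is unclear because the time limit is attached to stopping, and the text does not say whether it also limits the switch.

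**4. Size for LDA.** The documents give neither a switch rate nor the spread of visit times. Assume a constant switch hazard h of 1% to 3% per month and visit times that are uniform, or triangular with the peak at the nominal month. For a visit at V and nominal month m, the share of all patients who switch after m but before the visit is the average of exp(−hm) − exp(−hV) over V > m, counting zero otherwise.

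- Month 6: 0.5% (triangular, h = 1%) to 1.8% (uniform, h = 3%). For the upper figure: (1/6) × [3 × 0.8353 − (0.8353 − 0.7634)/0.03] ≈ 0.018.
- Month 12: 0.5% to 1.8% by the same formula.

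These are ceilings, since they ignore the protection in step 3. Assume that 50% to 80% of switches occur at registry visits, so 20% to 50% remain exposed:

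- low: 0.5% × 0.2 = 0.1% of patients
- high: 1.8% × 0.5 = 0.9% of patients

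Assume that 20% to 40% of those reach CDAI ≤10 on the new drug:

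- low: 0.1% × 0.2 = 0.02 points
- high: 0.9% × 0.4 = 0.36 points, at most about 6 of 1650 or 4 of 1223 patients

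With no protection at all, the upper figure is 1.8% × 0.4 = 0.7 points. The LDA denominator is restricted to baseline CDAI >10 and its size is not stated, so the patient counts are upper figures.

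For scale, the 95% CI half-width is 1.96 × √[p(1 − p)/n]. With an assumed p of 30% to 40% and 70% to 100% of patients eligible, it is 2.2 to 2.8 points at 6 months and 2.6 to 3.3 at 12 months.

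**5. Remission at 12 months.** Take baseline CDAI 20, stop and switch at month 8, and CDAI 2 on the new drug at month 12. For LDA the patient stopped within 12 months and switched: non-responder. For remission the patient did not stop within 6 months: responder. Under the same hazards the share switching between months 6 and 12 is exp(−6h) − exp(−12h), or 5.5% to 13.8%. Those switching between months 6 and 10, before the 12-month window opens, make up exp(−6h) − exp(−10h), or 3.7% to 9.4%; for them visit selection gives no protection. Their remission rate is not in the documents. At an assumed 10%, the 5.5% to 13.8% would add 0.5 to 1.4 points to the 12-month remission rate.

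**The case against.** **The examples are mostly protected.** Protocol 9.4 brings a registry visit when a new eligible drug is started at an office visit, and the closest-visit rule then prefers that visit. This stands, and it is why the effect is small. It does not cover a switch made between registry visits or a switch visit without CDAI. The SAP's own baseline definition provides for tofacitinib being started between visits, so the same must be expected of the next drug.

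**The time limit may be shorthand for the visit.** SAP 2.4.4 speaks of a visit at 6 months and puts 3–9 months in brackets, and SAP 2.5.2 moves freely between the month and the visit. That may be the intent, and the remission rule may likewise be meant for both time points. The SAP says neither, and a programmer could code month 6, month 9 or the visit date, each with a different result.

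**Three stronger readings are tempting and not supported.**

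- A reader might infer that a patient in LDA at month 4 who switches at month 5.5 is wrongly made a non-responder. Counting anyone who abandons the drug by month 6 as a 6-month failure is a coherent composite definition, not an error.
- A reader might infer that the change-in-CDAI rule is unbounded. Its bullet concerns change to the 6- or 12-month follow-up visit, which bounds it by implication; it only needs saying.
- A reader might infer bias between cohorts. No figure in the documents shows that visit timing or between-visit switching differs by line, dose or period.

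**Conclusion.** The point holds in limited form. Followed literally, the primary rule can score a response on another drug as tofacitinib LDA when a patient stops and switches between registry visits after the nominal month and before the selected visit. Where this happens, it can only raise the reported rate.

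The likely size is well under 1 point, about 0.02 to 0.4, and below the CI half-width. That rests on assumed values for the switch hazard, visit spread, share of switches at registry visits and response on the next drug. It would not be right to conclude that the LDA rate is materially inflated, or that late-window switchers in general are misclassified.

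The literal contradiction between 12-month LDA and 12-month remission does not depend on visit timing and could affect more patients. Its size also rests on assumption, and it disappears if the remission rule was meant to cover both time points. Both matters should be settled in the SAP; neither threatens a descriptive study as a whole.

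**What to change.** In SAP 2.5.2:

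1. For LDA and remission, at both time points, define as non-responders the patients who both discontinue tofacitinib and switch to another biologic or JAK inhibitor by the nominal month, or at any time before the selected visit, whichever is later. This keeps the composite definition for early switchers, closes the late part of the window, and settles the early stop with a late switch.
2. Name both 6 and 12 months in the remission rule.
3. State how a switch made at the selected visit itself is scored. The CDAI that day still reflects tofacitinib, yet the patient is leaving the drug. Either choice can be defended, but it should be the same whether the visit falls before or after the nominal month.
4. For change in CDAI, limit use of the switch-visit value to switches up to the selected visit.

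The cost is a few sentences of SAP text and one changed date comparison in the program. Visit dates and drug stop and start data are already needed for the current rule. The reported response rates may come out slightly lower.
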